General Background: Binge drinking is a major public health problem in the United States. The Center for Disease Control (CDC) places alcohol as the number three cause of preventable deaths following nicotine use and overweight (Mokdad et al, 2004). Binge drinking, generally defined as the consumption of five or more standard drinks for a man or four or more drinks for a woman in about a two hour period (see Courtney and Polich 2009), is a major component of excessive alcohol use and a serious problem for the United States. The CDC (2012) report indicated that 17.1% of the adult U.S. population reported one binge drinking episode in the past 30 days in 2010--men (23.2%) vs. women (11.4%) with peak ages 18-24 years (28.2%), 25-34 years (27.9%), and 35-44 years (19.2%). Men reported an average of 5 binge drinking episodes/month with a mean of 9.0 drinks/episode and women 3.2 binge drinking episodes/month at 5.9 drinks/episode. Binge drinking leads to multiple problems, e.g. accidental injury (Gmel et al, 2006), aggressive and violent behavior (Shepard et al, 2006), and high blood pressure (Fan et al, 2008). Additionally, there is increased risk for developing alcohol dependence in individuals that binge drink frequently (Hingson et al, 2006). Overall, binge drinking contributes to more than half of all deaths attributed to alcohol and to three quarters of the economic cost of excessive alcohol use—*binge drinking is a serious public health problem and one that may exceed traditionally defined alcohol dependence in its overall cost to society.*

Binge drinking is a complex construct as it is both a stand-alone phenomenon and also a component of alcohol use disorders. We are focusing on the behavior to allow greater fidelity to the preclinical data where the key behavior was consumption of an intoxicating amount of alcohol in a two hour period, a non-dependent model (Navarro et al, 2015). The majority of binge drinkers do not have physical dependence (see Woerle et al, 2007), and we are particularly interested in this “developmental” phase towards overt physical dependence as the preclinical literature suggests this phase may be a key time for clinical intervention (Thiele 2012).

Treatment of Binge Drinking with or without Co-Occurring Alcohol Use Disorders

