Pharmacotherapy approaches to treat binge drinking: Few clinical trials for binge drinking per se have been completed. O'Malley et al (2015) studied 128 young adult college students with heavy drinking (≥ 4 heavy drinking days in 4 weeks; ~60% DSM-IV alcohol dependent but without physical dependence) and compared 25 mg daily + 25 mg targeted naltrexone to be taken in anticipation of a heavy drinking episode to placebo. They did not find evidence for an effect on %heavy drinking or %abstinence but naltrexone led to a reduction in drinks/drinking day. They noted, "...the risk-benefit ratio favors offering young adult drinkers naltrexone to reduce the amount of alcohol they drink." Three trials have been conducted for older heavy drinkers or problem drinkers, mean age late 40's, using the opioid antagonists naltrexone (Kranzler et al 2003, 2009) or nalmefene (Karhuvaara et al, 2007). These trials sought individuals who were problem drinkers or heavy drinkers rather than physically dependent on alcohol, though 84-95% met criteria for DSM-IV alcohol dependence. These trials excluded individuals with evidence of more severe alcohol dependence, i.e. >4 DSM-IV criteria for dependence or having a history of alcohol withdrawal. All three trials found evidence for modest benefit. Taken together, these studies indicate that medications can be effective in the treatment of the milder end of the spectrum of alcohol use disorders where many binge drinkers are categorized. Pharmacotherapy for binge drinking is clearly in its infancy, perhaps in a similar state to pharmacotherapy for traditionally defined alcohol dependence 20 years ago when naltrexone was first discovered.

The current proposal will conduct the first human trial to test the novel preclinical finding that activating melanocortin systems in brain with/without opioid blockade potently reduces binge drinking. Identification of a potential efficacy signal would be significant as it would not only demonstrate that activation of melanocortin systems with/without opioid blockade has potential for therapeutic application for binge drinking in humans but would increase awareness of a biomedical component of binge drinking which could positively affect medical clinicians' attitudes and potentially increase identification and treatment efforts.

Innovation

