Participants: 12 men and women between the ages of 21 and 44 years of age will be recruited from social media, e-mail list serve to UNC students and staff, and local newspaper/radio advertisements. **Key Inclusion criteria:** 1) A minimum of 5/3 (men/women) or more binge drinking episodes per month over the past three months (mean population values, CDC (2012)). A binge drinking episode is defined as the consumption of 5/4 (men/women) standard drinks (~12 gms ethanol) in about a two-hour period. Requiring multiple episodes of binge drinking over several months is important to identifying subjects with a consistent pattern of binge-drinking as shorter time frames may give misleading information (see Courtney and Polich, 2009). Subjects may meet DSM-V criteria for mild or moderate alcohol use disorder; 2) BMI ≥ 18.5 (normal weight or above); 3) express a desire to achieve abstinence or to reduce alcohol consumption. **Exclusion criteria:** 1) Presence of physical dependence on alcohol as assessed by clear tolerance to alcohol or alcohol withdrawal symptoms based on SCID interview or a Severe Alcohol Use Disorder (>5 SCID DSM-V symptoms); 2) a history of bulimia or a seizure disorder; 3) clinically significant medical disease that might interfere with the evaluation of the study medication or present a safety concern (e.g., renal insufficiency, cirrhosis, unstable hypertension, diabetes mellitus); 4) clinically significant psychiatric illness including any psychotic disorder, bipolar disorder, anorexia/bulimia, severe depression, or suicidal ideation; 5) other substance abuse or dependence disorder other than nicotine or occasional cannabis use; 6) Concurrent use of anticonvulsants, opioids, varenicline, MAOIs, any anti-alcohol medication or any psychotropic medication with the exception of stable doses of antidepressants for one month; prior history of adverse reaction to bupropion or naltrexone; 7) AST or ALT > 3.5 times ULN or bilirubin $> 1.5 \times$ ULN; 8) positive urine toxicology screen with the exception of cannabis. Individuals with positive cannabis screens will be excluded only if they have a history of a cannabis use disorder; 9) pregnancy or breastfeeding.

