Trial Design: The design is an open-label trial. We will use standard clinical doses of bupropion-XL 300 mg/d (lower seizure risk) and naltrexone 50 mg/d dispensed by the UNC Investigational Drug Services. Bupropion XL will be initiated at 150 mg/d on Days 1-4 and increased to 300 mg/d for Days 5-84. Naltrexone will be initiated at 25 mg/d from Days 7-9 and then go to 50 mg/d for Days 10-84. We will see subjects at screening and then at Weeks 0, 1, 3, 5, 8 and 12. Subjects will be breathalyzed and receive Medical Management (MM) counseling to encourage compliance and progress towards drinking goals. MM is a medically oriented brief (10-15') therapy provided by medical personnel (MDs or nursing staff, only MDs in this trial). Our medical staff have been trained in MM and have been using it in other trials over the past five years. We will use the Time Line Follow-Back approach to assess alcohol consumption history modified to include time taken to consume alcohol and define a binge. We will also measure craving for alcohol using the Penn Alcohol Craving Scale.. We will assess tolerability by probing for adverse effects and will assess AST and ALT.

Our key outcomes of interest include tolerability and acceptability, drinking behavior including frequency and intensity of binge drinking, and craving for alcohol.

Recruitment, Telephone Screen, and Full Eligibility Screening: Subjects will initially be prescreened by phone and then at full screening read and sign the informed consent. A breathalyzer test will be administered (must be 0.00 gms/dl to give informed consent), height, weight and BMI recorded and a medical history and examination completed. Over-the-counter and prescription medication use will be recorded and nicotine use

Medical Management Intervention: The psychosocial support for the study will be Medical Management (MM) (Pettinati et al, 2005). Drs. [name], [name], [name] and [name] will conduct MM. Drs. [name] and [name] have been trained in MM by [name] and again by [name] of the University of Pennsylvania where [name] was trained as well. [name] has been trained in MM by [name]. MM sessions average 10-15 minutes and focus on three main areas: (1) feedback on consequences of drinking; (2) encouraging compliance with medication/addressing compliance problems and (3) encouraging progress towards drinking goal— reduction or abstinence are acceptable. 10% of sessions will be audiotaped and reviewed to enhance fidelity.

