Medication Compliance Monitoring: Participants will record their pill taking in calendar-style diaries that will be provided and collected at each visit. Pills will be distributed in blister packs that will be returned to the study coordinator to reconcile any unused medication from the returned blister packs with participants' diary records.

Statistical Plan and Data Analysis: The primary outcomes of interest are rates of adverse events, reported tolerability and retention. Frequency and intensity of binge drinking and craving for alcohol will also be recorded. Because this is an open-label feasibility trial, no statistical analyses are proposed but rather an overall assessment of tolerability and feasibility will be obtained. Data will be entered into an Excel database and reviewed for accuracy.

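### Does the undefined term for intensity of binge drinking oblige the plan to add total drinks per week?

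*Combined protocol and SAP*

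**What the plan says.** The Trial Design section names as key outcomes tolerability and acceptability, together with "drinking behavior including frequency and intensity of binge drinking, and craving for alcohol". Statistical Plan and Data Analysis makes adverse event rates, tolerability and retention primary. It then adds "Frequency and intensity of binge drinking and craving for alcohol will also be recorded", and says that no statistical analysis is proposed because this is an open-label feasibility trial. Neither section gives intensity a unit, a formula or a time window.

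Three other places bear on how the word would be read:

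- **Participants** sets the threshold: "A binge drinking episode is defined as the consumption of 5/4 (men/women) standard drinks" in about two hours. Entry requires "A minimum of 5/3 (men/women) or more binge drinking episodes per month over the past three months".
- **General Background** reports binge size per episode: "Men reported an average of 5 binge drinking episodes/month with a mean of 9.0 drinks/episode". For women it gives 3.2 episodes a month at 5.9 drinks each.
- **Trial Design** names the source of the drinking data: "We will use the Time Line Follow-Back approach to assess alcohol consumption history", modified to record the time taken to drink. **Medical Management Intervention** says of the drinking goal that "reduction or abstinence are acceptable".

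**The concern.** The natural reading of intensity is drinks per binge, as in General Background. That quantity is an average over only those occasions that still reach the threshold, which has three awkward consequences. It has a floor at 5 or 4 drinks. It has no value for someone who stops bingeing, which is a result the trial hopes for, so the participants who respond best would drop out of the summary. And it can rise while drinking falls, if the smaller binges disappear and the largest remain.

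At stake is how the drinking results would read. The background section on pharmacotherapy hopes for a possible efficacy signal. It also cites a naltrexone trial in young heavy drinkers in which the choice of measure mattered: "They did not find evidence for an effect on %heavy drinking or %abstinence but naltrexone led to a reduction in drinks/drinking day". If intensity understates a real reduction, or rests on different people before and during treatment, a reader could be misled about how much less the 12 participants drank. Total drinks per week, scored zero for abstainers, would avoid the floor and the missing values.

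**Working it through.** The plan states no figure for this outcome, so there is none to reproduce. The inputs are the thresholds 5/4 and entry minimums 5/3 per month (Participants), and the means 9.0 and 5.9 drinks per episode (General Background).

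**1. Floor.** Largest possible fall = 1 − threshold/mean.
- Men: 1 − 5/9.0 = 44.4%
- Women: 1 − 4/5.9 = 32.2%

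**2. A uniform cut.** Assumptions: drinks per occasion X follow a gamma or lognormal distribution with coefficient of variation (CV) 0.3, 0.4, 0.5, 0.6 or 0.7; the mean is set so that E[X | X ≥ threshold] equals 9.0 or 5.9; every occasion shrinks by the same proportion; the two-hour window is ignored. Intensity is E[X | X ≥ threshold], and frequency is proportional to P(X ≥ threshold). Drinks taken in binges are the product of the two.

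One setting in full (men, gamma, CV 0.3, mean 8.74, 40% cut): intensity goes from 9.0 to 6.42, a fall of 28.6%. P(X ≥ 5) goes from 0.945 to 0.523, a fall of 44.7%. The product falls by 1 − 0.714 × 0.553 = 60.5%.

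Ranges over the ten settings for each sex:

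| Fall in | Men, 40% cut | Women, 40% cut | Men, 25% cut | Women, 25% cut |
|---|---|---|---|---|
| Intensity | 16.4–28.6% | 9.8–20.6% | 10.5–19.5% | 6.2–14.3% |
| Frequency | 44.7–58.0% | 74.5–76.6% | 17.8–35.0% | 40.8–52.8% |
| Drinks in binges | 60.5–64.9% | 78.6–80.0% | 33.8–41.9% | 49.3–55.7% |

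Intensity falls in every setting. It falls by less than the true cut, while drinks in binges falls by more. Total drinks falls by exactly 40% or 25%, but only because the cut was assumed uniform.

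**3. No value.** With Poisson counts starting at the entry minimum, P(no binge) = exp(−expected binges). After the 40% cut the expected monthly number is 2.10–2.77 for men and 0.702–0.765 for women.
- One month: men exp(−2.77) to exp(−2.10) = 6–12%; women exp(−0.765) to exp(−0.702) = 47–50%.
- All 84 days, multiplying by 84/30.4 = 2.763: men exp(−7.65) to exp(−5.80), at most 0.3%; women exp(−2.11) to exp(−1.94) = 12–14%.

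The one-month figures depend on a reporting window the plan does not specify. Both sets start from the lowest rate that allows entry.

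**4. Can intensity rise?** Five occasions of 7, 7, 7, 7 and 17 drinks average 45/5 = 9.0. If they become 4, 4, 4, 4 and 12, a man has one binge of 12, so intensity rises to 12.0 while total drinks fall by 1 − 28/45 = 38%. The example needs unequal cuts (43% on the small occasions, 29% on the large one), which lie outside the model in step 2. Frequency falls from 5 to 1 in the same example.

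**5. The proposed replacement.** A man who drinks 6 drinks in two hours and later spreads the same 6 over five hours has stopped bingeing by the trial's definition. Binge frequency registers this; total drinks per week does not.

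**The case for a change.** The strongest case for a change is this. The floor and the missing value need no modelling; they follow from the trial's own definition of a binge. Drinking is called a key outcome, and descriptive summaries are all the trial will report on it. Frequency counts threshold crossings and not amount: in the table above it overshoots the true cut for women while intensity undershoots it. Naming the measure beforehand costs one sentence, and in an open-label group of 12 it would prevent choosing the measure after the results are seen.

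Much of this stands. The word is undefined, and drinks per binge would be a poor summary if shown alone. But the plan does not show it alone, and it attaches no test, comparison or decision rule to it. Frequency and drinks per binge together give drinks taken in binges, which is zero for a participant with none and so exists for everyone with data. The argument about selective choice has little force where no efficacy claim is planned. Nor is total drinks plainly the better main measure: General Background says the trial targets an intoxicating amount within two hours, as in the animal model, and step 5 shows that weekly totals can miss a change in that behaviour. On the other side, the mouse results under Innovation 1 are expressed as ethanol consumption, so overall amount is not irrelevant.

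**Conclusion.** The concern is accurate about the wording but does not call for a change. Intensity is an undefined term in a secondary, descriptive outcome, and the defect arises only on a reading that the plan does not state, although it is the likely one. On that reading the measure is capped at a 44% fall in men and 32% in women, and under the assumed uniform 40% cut it would show about 16–29% and 10–21%. Those percentages rest on survey means standing in for participants, the assumed distributions and the uniform cut; the cap itself needs only the survey means and the threshold.

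Analysts can fill the gap sensibly when they report: say what intensity means, state how many participants contribute, and read it beside frequency scored zero where there are no binges. The word "including" in the outcome list leaves room for weekly totals as well. They could be drawn from the Time Line Follow-Back, provided daily drink counts are kept; the text implies this without saying so outright. Making total drinks the main measure of amount would be a matter of preference, trading one blind spot for another. The trial's conclusion on adverse events, tolerability and retention is the same either way.
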